	
will be used in Part 2. SMC meeting minutes and outputs provided for these SMC meetings will be documented and archived.
 
Exploratory analyses of PK/PD may be performed at the end of Part 1 and additionally if considered informative for the study.
 
Part 2:
 
In Part 2 we are randomizing 200 patients. 40 patients for the each of the cohorts A and B, and 30 patient for each of the cohorts C, D, E and F. An interim futility analysis will be performed for cohort C, D, E and F in Part 2. Until any decision from the futility analysis is done, the enrolment of next patient will not be stopped. The two-stage design is planned to stop further recruitment of patient if the defined efficacy boundary (see Table 7.7.2: 1) is not met at the first stage.
 
The interim analyses for each cohort will be conducted after 15th patients in that cohort have completed their two on-treatment imaging assessment (i.e. end of cycle 4).
 
In addition, if considered necessary interim analysis may be performed for evaluation of the efficacy and safety aspects as each cohort is finished

Rationale for change	Adaption to the new requirements
Section to be changed	7.7.1
Description of change	
Change from:
 
For Part 1, no formal statistical power calculations of sample size were performed. Approximately 20-25 patients will be expected for the dose finding part and confirmation of RP2D. Fewer patients might be needed based on the recommendation of the SMC and the actual number of cohorts tested.
 
To:
 
For Part 1, no formal statistical power calculations of sample size were performed. Approximately 12-18 patients will be expected for the dose finding part and confirmation of RP2D. Fewer patients might be needed based on the recommendation of the SMC and the actual number of cohorts tested.

Rationale for change	Adaption to the new requirements
Section to be changed	7.7.2

Description of change	
Changed from: For Part 2, it is assumed that BI 836880 in combination with BI 754091 will have an ORR of at least 30% in patients with locally advanced or metastatic non-squamous NSCLS with low PD-L1 expression. For a cohort with 30 evaluable patients, an ORR of greater than 25% would be observed with a probability of approximately 72% assuming a true response rate of 30%. The probability of observing a false positive signal, i.e., to observe an ORR of more than 25% if the underlying true ORR is 10%, is around 1%. In patients with high PD-L1 expression, it is assumed that BI 836880 in combination with BI 754091 will have an ORR of at least 50%. For a cohort with 30 evaluable patients, an ORR of greater than 45% would be observed with a probability of approximately 71% assuming a true response rate of 50%. The probability of observing a false positive signal, i.e., to observe an ORR of greater than 45% if the underlying true ORR is 30%, is around 4%. Table 7.7.2: 1 summarizes the probability of observing certain ORRs based on different assumption of the underlying ORR.
 
Table 7.7.2: 1 Probabilities of observing certain objective response rates Table not shown because of format reasons
 
To: For Part 2, below cohorts are assume:
 
• Cohort A: patients with locally advanced or metastatic non-squamous Non-Small Cell Lung Cancer with CPI monotherapy• Cohort B: patients with locally advanced or metastatic non-squamous Non-Small Cell Lung Cancer pre-treated with a combination of platinum-based chemotherapy and checkpoint inhibitor• Cohort C: patients with locally advanced or metastatic Small Cell Lung Cancer, with no more than one line of chemotherapy• Cohort D: patients with histologically confirmed recurrent glioblastoma (primary), with no more than one line of chemotherapy (concurrent and adjuvant temozolomide based chemotherapy)• Cohort E: patients with histologically confirmed, unresectable, Stage IV metastatic melanoma, with least one line of any kind of immune therapy• Cohort F: patients with locally advanced or metastatic and/or unresectable Hepatocellular Carcinoma (HCC) who were intolerant or progressed during 1st line sorafenib or lenvatinib treatment; subsequent CPI therapy is allowed as the most recent anticancer treatment. 
A total of approximate 200 patients will be enrolled for these 6 cohorts. 40 patients each are planned for cohort A and B and 30 patients each are planned for cohort C to F.

------------------------------	---

	
For cohorts A, B, and E (MLN), there is no literature available for the target patients. As there are no treatments of proven efficacy for this population, it is assumed around 5% ORR with background therapy. The futility boundary for cohort E is set as 7% at planned interim futility analysis timing. The early stopping probabilities are shown in Table 7.7.2: 1.
 
For cohort C (SCLC), around 20% ORR with anti-PD-1 antibody monotherapy is assumed. In Checkmate-032 (R19-1713) which is an open label phase I/II trial of Nivolumab in patients with SCLC who experienced disease progression after platinum-based chemotherapy, the ORR was 12% [95%CI, 6.5-19.5] (N=109). In KEYNOTE-158 (R19-1713), which is a phase II basket study of Pembrolizumab, patient with advanced SCLC had an ORR of 18.7% [95%CI, 11.8-27.4] (N=107). In KEYNOTE-028 (R19-1713), which is a phase Ib basket trial, patients with extensive-stage SCLC showed an ORR of 33% [95%CI, 16-55] (N=24). Based on above result, the futility boundary for cohort C is set as 20% at planned interim futility analysis timing.
 
For cohort D (GBM), around 25% ORR with Bevacizumab is assumed. In AVF3708 (R11-2708), which is an open-label study in patients with glioblastoma who had progressed following initial treatment with temozolomide and radiation, the ORR was 28% [95%CI, 19-40] (N=85). Based on above results, the futility boundary for cohort D is set as 25% at planned interim futility analysis timing.
 
For cohort F (HCC), around 15% ORR with anti-PD-1 antibody monotherapy is assumed. In Checkmate-040 (R17-3829) which is an open label phase I/II trial of Nivolumab in patients with advanced hepatocellular carcinoma, the ORR was 20% [95%CI, 15-26] (N=50) in dose expansion phase and 15% [95% CI, 6-28] (N=10) in the dose escalation phase. In KEYNOTE-224 (R19-0168) which is a phase 2 study of Pembrolizumab in patients with advanced hepatocellular carcinoma previously treated with sorafenib , the ORR was 17% [95% CI, 11-26] (N=104). Based on above result, the futility boundary for cohort F is set as 15% at planned interim futility analysis timing.
 
Different homogeneous scenarios and heterogeneous scenarios as well as different sample sizes are considered in the simulations to assess the frequentist operating characteristics of the BHM approach. The simulation results as shown in Table 7.7.2: 2 below show that, with the proposed cohort size, the BHM approach has reasonable probability of reaching the pre-specified response rate under a wide range of scenarios.

--	---

	
Table 7.7.2: 1 Early stopping probabilities at interim based on observed ORR under different scenarios
 
Table 7.7.2: 2 Operating characteristics of the Bayesian Hierarchical Modelling approach for final analysis under different scenarios with interim analysis based on observed ORR
 
Tables not shown because of format reasons

Rationale for change	Adaption to the new requirements
Section to be changed	9.2
Description of change	
Added information c23621412-01
 
[REDACTED] A First in human Phase I, non-randomized, open label multi-center dose escalation trial of BI 836880 administered by repeated intravenous infusions in patients with solid tumors. 1336.1 30 April 2019

Rationale for change	New available information
Section to be changed	9.1.
Description of change	
Added information:
 
 
 

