[Part 2 of 2 of the document. The other parts are not shown.]

	
2. Documented disease progression or relapse (based on investigator's assessment) during or after completion of at least 2 cycles of platinum-based chemotherapy as first line treatment of Stage IIIB/IV NSCLC. This includes patients relapsing within 6 months of completing (neo)adjuvant/curative-intent chemotherapy or chemoradiotherapy
 
To:
 
1. No previous treatment with check-point inhibitor. Or patients with CPI based treatment as last therapy before entering the trial.2. Documented disease progression or relapse (based on investigator's assessment) during or after completion of at least 2 cycles of platinum-based chemotherapy as first line treatment of Stage IIIB/IV non- squamous NSCLC or for CPI experienced patients during or after completion of at least 2 cycles of platinum-based chemotherapy and a CPI treatment (monotherapy or in combination with chemotherapy). This includes patients relapsing within 6 months of completing (neo)adjuvant/curative-intent chemotherapy/CPI or chemoradiotherapy
Section to be changed	3.3.3 Exclusion Criteria
Description of change	8. Patients with personal or family history of QT prolongation and/or long QT syndrome, or prolonged QTcF at baseline (> 470 ms). Changed to: 1. Patients with personal or family history of QT prolongation and/or long QT syndrome, or prolonged QTcF at baseline (> 480 ms).
Rationale for change	Clarification of the QTcF
Rationale for change	Adaption regarding the new population
Section to be changed	3.3.4.1 Withdrawal from trial treatment
Description of change	Added information: 
• The patient can no longer be treated with trial drug after a drug related Adverse Event CTCAE Grade 4.

	
• The patient can no longer be treated with trial drug after a DLT, which did not recover to CTCAE Grade 1 or pre-treatment values within 2 weeks.
Rationale for change	Request by the German EC
Section to be changed	4.1.1 Identity of the Investigational Medicinal Products

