Description of change	
In this trial the IMP BI 836880 will be switched to a new pharmaceutical formulation which is diluted in a standard 5% Glucose/Dextrose solution. The new formulation will be made available in this trial at the latest before expiry of the old formulation prepared with a drug specific Diluent. Details of the trial medications, BI 836880, BI 754091, and respective diluents, are presented in Tables 4.1.1: 1 and 4.1.1:2, in the IB's for BI 836880 and BI 754091 as well as in the Instruction for the Pharmacist (IfP).
 
Deletion of Table 4.1.1: 2

Rationale for change	Change of the IMP formulation BI 836880. Diluent will not be used anymore with the new formulation.
Section to be changed	4.1.4 Re-treatment criteria
Description of change	
Adding of information: In case of a DLT (drug related AEs CTCAE Grade 3, 4 according to Table 5.2.6.1: 1) the patient will discontinue treatment.
 
Once a DLT has recovered to CTCAE grade 1 or pre-treatment values, the study drugs may be restarted at a lower dose level in case the patients benefits from the study drug after discussion between investigator and Clinical Monitor at Boehringer Ingelheim
 
And change of
 
• QTcF <=470 ms (according to Exclusion-Criterion #8) 
To:
 
• QTcF <=480 ms (according to Exclusion-Criterion #8)
Rationale for change	Request by German EC, clarification on the QTcF
Section to be changed	4.1.7 Storage condition
Description of change	Change from:

	
BI 836880 vials and Diluent Buffer vials and BI754091 vials must be stored in their original packaging.
 
To:
 
BI 836880 vials (old and new formulation) and BI754091 vials must be stored in their original packaging.

Rationale for change	Adaption regarding new IMP formulation
Section to be changed	5.2.2 Body temperature
Description of change	
Change from:
 
Not acceptable/preferred methods include: IR-measurement in ear, forehead or temple.
 
To:
 
Not preferred methods but accepted include: IR-measurement in ear, forehead or temple.

Rationale for change	Clarification
Section to be changed	5.2.3 Safety laboratory parameter

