		
corticosteroid therapy and/or hormone replacement therapy.
 
○ Grade 3 or 4 elevation in serum amylase and/or lipase that is not associated with clinical or radiographic evidence of pancreatitis○ Grade 3 nausea or vomiting that lasts <48 hours, and resolves to ≤Grade 1 either spontaneously or with conventional medical intervention○ Alopecia○ Grade 3 fatigue that persists less than 7 days○ Grade 3 infusion related reaction which can be controlled by appropriate medication according to investigator's decision, and the subsequent infusion will not be delayed for more than two weeks.○ Grade 3 rash that resolves to ≤ Grade 1 within 2 weeks○ Grade 3 or 4 elevation in serum amylase and/or lipase that is not associated with clinical or radiographic evidence of pancreatitis○ Grade 3 endocrine disorders (thyroid, pituitary, and/or adrenal insufficiency) that are managed with or without systemic corticosteroid therapy and/or hormone replacement therapy, and the patient is asymptomatic.○ Grade 3 tumour flare. 
Laboratory toxicity
 
● Hypertension: systolic blood pressure >=160 mm Hg or diastolic blood pressure >=100 mm Hg, confirmed by second measurement of an additional set of 3 BP measurements, or 3 sequential ambulatory blood pressure measurements when indicated (e.g. white coat effect), and which cannot be controlled by hypertensive medication and which requires a dose reduction / discontinuation of trial medication(s)● Grade >=3 proteinuria (urinary protein ≥ 3.5 g/day)
--	--	---

To:

The occurrence of any of the toxicities presented in [Table 5.2.6.1: 1](#) will be considered a DLT, if assessed by the investigator to be related to the administration of either of the study drugs. All DLTs occurring during Part 1 of the study will be considered an AESI and reported on the SAE form.

Incidence and severity of adverse events will be graded according to the common terminology criteria for adverse events (CTCAE, version 5.0),

Table 5.2.6.1: 1 Dose Limiting Toxicities
(according to CTCAE V5.0)

Drug related toxicity category	Criteria defining a DLT*

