Hematologic	
Grade 4 neutropenia (<500/mm³) lasting ≥5 days or complicated by infectionGrade ≥ 3 documented infection with neutropenia.Grade ≥ 3 febrile neutropenia (ANC<1000/mm³ complicated by fever ≥38.3 °C or 101°F° C or a sustained temperature of ≥38.0C (100.4 ° F) for more than 1 hour.Grade 3 thrombocytopenia (≥ 25,000/mm³ and <50,000/mm³) associated with bleeding or requiring platelet transfusion.Grade 4 thrombocytopenia (<25,000/mm³). Grade 4 anaemia (i.e., life-threatening consequences or urgent intervention indicated).

Table 5.2.6.1: 1 Dose Limiting Toxicities
(according to CTCAE V5.0) (cont'd)

Drug related toxicity category	Criteria defining a DLT*
Non-hematologic	Non-laboratory toxicity 
Any Grade 4 or 5 AE other than disease progression.Any Grade 2 drug-related uveitis or eye pain or blurred vision that does not respond to topical therapy and

		
does not improve to Grade 1 severity within 2 weeks or requires systemic treatment.
 
• Any treatment-related Grade ≥ 2 toxicity that occurred during Cycle 1 that persists and results in an inability to administer BI 754091 or BI 836880 on Cycle 2 Day 1.• any grade ≥ 2 pneumonitis of any duration• Any toxicity Grade ≥ 3 toxicity except:
○ Grade 3 immune-related AE that resolves to \leq Grade 1 or to baseline with immunosuppressive therapy within 2 weeks○ Grade 3 asymptomatic endocrine disorders (thyroid, pituitary, and/or adrenal insufficiency) that are managed with or without systemic corticosteroid therapy and/or hormone replacement therapy.○ Grade 3 or 4 elevation in serum amylase and/or lipase that is not associated with clinical or radiographic evidence of pancreatitis○ Grade 3 nausea or vomiting that lasts <48 hours, and resolves to \leq Grade 1 either spontaneously or with conventional medical intervention○ Alopecia○ Grade 3 fatigue that persists less than 7 days○ Grade 3 infusion related reaction which can be controlled by appropriate medication according to investigator's decision, and the subsequent infusion will not be delayed for more than two weeks.○ Grade 3 rash that resolves to \leq Grade 1 within 2 weeks○ Grade 3 endocrine disorders (thyroid, pituitary, and/or adrenal insufficiency) that are managed with or without systemic corticosteroid therapy and/or hormone replacement therapy, and the patient is asymptomatic.○ Grade 3 tumour flare.

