	
PART 1:
 
• Adverse events (AEs), drug related AEs, drug related AEs leading to dose reduction or discontinuation during treatment period.• Pharmacokinetic parameters C_{max}, t_{max}, AUC_{0-504h} after the first infusion cycle. 
PART 2:
 
• Adverse events (AEs), drug related AEs, drug related AEs leading to dose reduction or discontinuation during treatment period• Disease control (DC), defined as best overall response of CR, PR, or stable disease (SD) (RANO for GBM & RECIST1.1 for all other cohorts) from first treatment infusion until the earliest of disease progression, death or last evaluable tumor assessment before start of subsequent anti-cancer therapy, lost to follow-up or withdrawal of consent.• Duration of objective response (DoR), defined as the time from first documented CR or PR (RANO for GBM & RECIST1.1 for all other cohorts) until the earliest of disease progression or death among patients with OR.• Progression-free survival (PFS) (RANO for GBM & RECIST1.1 for all other cohorts), defined as the time from first treatment infusion until disease progression or death from any cause, whichever occurs earlier.• Tumour shrinkage (in millimeters), defined as the difference between the minimum post-baseline sum of diameters of target lesions (longest for non-nodal lesions, short axis for nodal lesions) and the baseline sum of diameters of the same set of target lesions in case of RECIST. In GBM, using RANO criteria, tumor shrinkage will be calculated based on the difference between the post-baseline and baseline measurements of the sum of product of the largest bi-dimensional measurements for all target lesions.• Pharmacokinetic parameters C_{max}, t_{max}, AUC_{0-504h} after the first and fourth infusion cycle.
Rationale for change	Information regarding RANO for GBM cohort D was added
Section to be changed	Synopsis – Number of patient entered
Description of change	Changed from:

	
A total of 255 patients (28 part 1 plus 227 part 2) approximately will be entered
 
(Part 1 and Part 2)
 
To:
 
A total of 315 patients (22 part 1 plus 293 part 2) approximately will be entered
 
(Part 1 and Part 2)
			
Rationale for change	Screening failure rate was increased, Part 1 patient # was adapted and additional patient for cohort G were added.			
Section to be changed	Synopsis – Number of patients on each treatment			

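### Part 1: the lower-dose restart after a recovered DLT in 4.1.4 carries neither the Grade 4 bar nor the 2-week recovery limit that the same amendment added to 3.3.4.1

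*Protocol*

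**What the plan says.** All texts below are incoming wording recorded in the protocol's amendment log.

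- **3.3.4.1, Withdrawal from trial treatment** (amendment logged before Global Amendment 3). Two bullets were added. The first reads: "The patient can no longer be treated with trial drug after a drug related Adverse Event CTCAE Grade 4". The second ends trial drug after a DLT that has not returned to Grade 1 or the pre-treatment value within 2 weeks. The reason given is a request by the German ethics committee.
- **4.1.4, Re-treatment criteria** (same amendment). The added text begins: "In case of a DLT (drug related AEs CTCAE Grade 3, 4 according to Table 5.2.6.1: 1) the patient will discontinue treatment". It then says that, on recovery to Grade 1 or baseline, "the study drugs may be restarted at a lower dose level in case the patients benefits from the study drug"; the investigator must first consult the sponsor's Clinical Monitor. The stated reason is "Request by German EC, clarification on the QTcF".
- **5.2.6.1, Dose limiting toxicities** (same amendment). A listed toxicity "will be considered a DLT, if assessed by the investigator to be related to the administration of either of the study drugs". The table includes "Any Grade 4 or 5 AE other than disease progression", as well as Grade 4 thrombocytopenia, Grade 4 anaemia and prolonged or complicated Grade 4 neutropenia.
- **4.1.4, Dose reduction guidelines, Part 1** (Global Amendment 3). Dosing stops temporarily for a DLT. It may continue after recovery sufficient to meet the re-treatment criteria, with BI 836880 one dose level lower, and ends if the DLT is irreversible. No grade and no time limit is given.

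**The concern.** These are patient-level safety stopping rules. Section 3.3.4.1 is absolute: it makes no exception for recovery and offers no reduced dose. The restart text in 4.1.4, where a site would look when deciding whether to re-dose, permits what 3.3.4.1 forbids and does not refer to it. A site working from 4.1.4 alone could, with the Clinical Monitor's agreement, restart a patient who should have been withdrawn. Both additions cite the same ethics committee, so the recorded rationale does not show which was meant to govern.

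**Working it through.** No figure is at stake, so the check is a comparison of rules.

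**Step 1: is there an overlap?** Under 5.2.6.1 an event is a DLT only if judged related to a study drug. Every Grade 4 DLT is therefore also a drug-related Grade 4 adverse event, which is the trigger in 3.3.4.1. The overlap is not empty: the table's Grade 4 cytopenias can recover, and recovery is the condition for the restart.

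**Step 2: apply both sections to each kind of Part 1 DLT.**

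| Event | 3.3.4.1 | 4.1.4 restart text | Result |
|---|---|---|---|
| Grade 3 DLT, recovered within 2 weeks | no bar | restart possible | consistent |
| Grade 3 DLT, recovered after 2 weeks | withdrawn | restart possible | conflict on time |
| Grade 4 DLT, recovered | withdrawn | restart possible | conflict on grade |
| DLT that never recovers | withdrawn | no restart | consistent |

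**Step 3: remove what other text settles.** Grade 4 infusion-related reactions are outside the overlap. Section 5.2.7 already required permanent discontinuation at Grade 4 or higher; Global Amendment 4 kept that, and Global Amendment 5 lowered the threshold to Grade 3. Part 2 is outside as well: Global Amendment 4 states that DLTs no longer apply there.

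**Step 4: does a later entry resolve it?** None shown does. The Part 1 guideline in Global Amendment 3 points to the re-treatment criteria, not to 3.3.4.1. Global Amendment 4 is shown only giving the Part 1 re-treatment criteria a new heading. No later entry shown changes 3.3.4.1.

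**Step 5: size.** The Global Amendment 4 synopsis says: "A total of 315 patients (22 part 1 plus 293 part 2) approximately will be entered". It gives 12 to 18 evaluable patients for Part 1. Section 1.4 as amended on 03 Mar 2020 reports 1 DLT in Part 1, at 360 mg, grade not stated. At 360 mg, Table 4.1.4: 1 says to stop BI 836880, so no lower dose of that drug was available to restart.

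**The case against.** The strongest objection is that the operative text of 3.3.4.1 and 4.1.4 is not shown. Section 4.1.4 was edited repeatedly, some log entries are blank, and two later amendments record unspecified editorial changes, so a cross-reference may already exist. This stands as a limit on certainty. It does not make the point a comparison of old text with new: the two sentences that collide entered together, in one amendment.

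Second, a reader might infer that 4.1.4 expressly allows restart after Grade 4. It does not. The grades appear in the sentence that stops treatment, which agrees with 3.3.4.1. The restart sentence names no grade and is conditional on recovery, benefit and discussion. The permission arises because Grade 4 is named and then not excluded.

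Third, the provisions can be read in sequence: Grade 4 means off drug, no recovery in 2 weeks means off drug, and the remaining DLTs may restart. That is probably what was meant, and a reader holding both sections would follow the stricter one. But 4.1.4 does not say so, and a discretionary permission still conflicts with an absolute bar.

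Fourth, little exposure may remain. The decision of December 2021 ended recruitment, and Global Amendment 7 capped treatment at 53 cycles of 3 weeks, or 53 × 3 = 159 weeks. If every Part 1 patient had started by 03 Mar 2020 (an assumption; the Part 2 dose had been selected by then), the cap falls in March 2023, before Global Amendment 8 of 03 May 2023. Dose delays, or extensions of up to 6 cycles, could carry a patient past it. The documents do not say whether any Part 1 patient was still on treatment. This reduces the consequence without removing the inconsistency.

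**Conclusion.** The point holds as a wording conflict of low impact. In Part 1, the restart text in 4.1.4 and the Part 1 dose reduction guideline leave out two limits that 3.3.4.1 imposes: no drug after a drug-related Grade 4 event, and none after a DLT unrecovered at 2 weeks. The grade conflict concerns recovered Grade 4 DLTs other than infusion-related reactions; the time conflict concerns DLTs that recover after 2 weeks.

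The conclusion assumes that both additions remain in the current protocol, which the log suggests but cannot prove. No patient is known to have been re-dosed contrary to 3.3.4.1. A reader might infer harm or a compromised analysis; the documents support neither. No endpoint, sample size or analysis depends on this wording.

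**What to change.** Let 3.3.4.1 prevail. In 4.1.4, limit the restart sentence to DLTs below Grade 4 that recover within 2 weeks, and add *subject to the withdrawal criteria in Section 3.3.4.1*. Make the same change in the Part 1 paragraph of the dose reduction guidelines; correcting only the restart sentence would leave the second route open. *Below Grade 4* is better than *Grade 3*, because the DLT table also contains some Grade 2 events. If the current text already has this cross-reference, nothing is needed.

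The cost is one limiting clause in each of two paragraphs, with no change to data collection or analysis.
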